6 ABBREVIATIONS AND DEFINITION OF TERMS

ADL	Activities of Daily Living
AESI	Adverse Events of Special Interest
ALS	Amyotrophic Lateral Sclerosis
BP	Blood Pressure
CAP	College of American Pathologist
CD	Cervical Dystonia
CFR	Code of Federal Regulations
CGI-C	Clinical Global Impression of Change
CGI-S	Clinical Global Impression of Severity
CIB	Clinical Investigator's Brochure
CLIA	Clinical Laboratory Improvement Act of 1988
C-SSRS	Columbia Suicide Severity Rate Scale
CRA	Clinical Research Associate
CRO	Clinical Research Organization
DFSS	Drizzling Frequency and Severity Score
DIS	Drizzling Impact Score
eCRF(s)	Electronic Case Report Form(s)
FDA	Food and Drug Administration
FVC	Forced Vital Capacity
GCP	Good Clinical Practices
HIPAA	Health Insurance Portability and Accountability Act
ICF	Informed Consent Form
ICH	International Conference on Harmonization
IND	Investigational New Drug
IRB(s)	Institutional Review Board(s)
LAR	Legally Authorized Representative
LD ₅₀	Median Lethal Dose
Max	Maximum
MCH	Mean Corpuscular Hemoglobin
MCHC	Mean Corpuscular Hemoglobin Concentration
MCV	Mean Corpuscular Volume
MedDRA	Medical Dictionary for Regulatory Activities
Min	Minimum
n	Number
NG	Nasogastric
PD	Parkinson's Disease
PEG	Percutaneous Endoscopic Gastrostomy
PGI-C	Patient Global Impression of Change
PGI-S	Patient Global Impression of Severity
RR	Respiration Rate
SAE(s)	Serious Adverse Event(s)
SD	Standard Deviation
SAP	Statistical Analysis Plan
TEAE(s)	Treatment-Emergent Adverse Event(s)

Temp	Temperature
ULN	Upper Limit of Normal
UPDRS	Unified Parkinson's Disease Rating Scale
US	United States
USFR	Unstimulated Salivary Flow Rate
VAS	Visual Analog Scale
WBC	White Blood Cell
Wk	Week

7 BACKGROUND AND SIGNIFICANCE

8 STUDY OBJECTIVES

8.1 Primary Objective

The primary objective of this study is:

- To determine the long-term safety and tolerability of MYOBLOC (administered intraglandularly as a single total dose of 3,500 Units) treatments every 13 weeks over a maximum possible duration of 1 year in adult subjects with troublesome sialorrhea.

8.2 Secondary Objective

The secondary objective of this study is:

- To assess the magnitude of therapeutic responses of MYOBLOC (administered intraglandularly as a single total dose of 3,500 Units) using effectiveness assessments performed at intervals after treatments every 13 weeks over a maximum possible duration of 1 year.

9 STUDY ENDPOINTS

9.1 Safety Endpoints

- Occurrence, seriousness, severity, and causality assessment of adverse events at each study visit;
- Occurrence of adverse events of special interest (i.e., aspiration, aspiration pneumonia, choking, dysphagia) at each study visit as assessed by the Investigator;
- Columbia Suicide Severity Scale (C-SSRS) at each study visit; and
- Occurrence of dental adverse events.

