Subjects whose risk of aspiration are judged by the investigator to be satisfactorily controlled by placement of PEG or G-tube for nutritional support are eligible to participate. Specific criteria excluding subjects with moderate to severe dysphagia or choking within the last 6 months prior to screening have been removed, and instead the protocol focuses solely on the risk of aspiration, taking into consideration that those with a PEG or G-tube (in whom placement of either would mitigate the risk of aspiration associated with a moderate to severe risk dysphagia or choking) may participate. The previous exclusion criteria could be considered too vague or restrictive as it focused on a symptom (dysphagia or difficulty with swallowing) that is common to many neurological disorders and especially frequent in ALS. The

revised inclusion/exclusion criteria now focus on the baseline risk of aspiration because it is aspiration that can lead to significant morbidity and even mortality.

- The requirement to administer the Visual Analog Scale (VAS) to subjects in order to rate severity for dysphagia and dry mouth at every clinic visit has been removed. Administering the scale at every visit, regardless of a reported event of dysphagia or dry mouth, is unnecessary and would result in an overreporting of events. Adverse events of dysphagia and dry mouth will continue to be collected based on subject report and severity will be determined by the Investigator.

Study drug injections should not be administered if an adverse event of dysphagia or dry mouth of moderate to severe severity persists without prior consultation with the Medical Monitor. If the adverse event has not resolved or has not improved to a mild severity by the end of the per protocol window for injections to occur (every 13 ± 2 weeks), the Medical Monitor should be contacted to discuss whether or not the subject should be dosed, discontinued, etc.

- Administrative updates have been incorporated, including a change in the Medical Monitor information.

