16 SAFETY ASSESSMENTS

16.1 Medical/Surgical/Medication History

The medical history (with demographic information, sialorrhea history with date of onset), should also include current co-morbidities, relevant past illnesses, all current medications (including those taken within 30 days before screening), surgical procedures performed within the prior 6 months, and past treatment(s) for sialorrhea.

As part of the screening medical history assessment and exclusion criteria review, subjects will be evaluated for presence or prior history of aspiration, aspiration pneumonia, choking, and/or dysphagia.

To ensure that these events are consistently rated across investigator sites, the definitions for the diagnosis and intensity provided in Section 16.2.4 should be used for

baseline evaluation and all subsequent assessments. The Investigator must determine, based on clinical evaluation, whether subsequent occurrences of aspiration, aspiration pneumonia, choking, and/or dysphagia during the study qualify as adverse events, as defined in Section 16.2.1.

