16.2.4 Adverse Events of Special Interest

Adverse events indicative of compromised airway protection as manifested by aspiration, aspiration pneumonia, choking, and dysphagia will be closely evaluated as adverse events of special interest (AESI). In order to properly evaluate the events pre-identified for compromised airway protection, a detailed baseline evaluation of the subject’s presence or

prior history of aspiration, aspiration pneumonia, choking, and dysphagia must be taken at screening and captured in the subject's source documents and eCRF.

To ensure that these events are consistently rated on the same criterion throughout the study, the definitions for diagnosis and intensity identified below should be used for baseline evaluations. This thorough baseline evaluation will assist the Investigator in determining, based on a clinical evaluation, whether or not occurrences of aspiration, aspiration pneumonia, choking, and dysphagia during the study qualify as adverse events, as defined in Section 16.2.1.

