3.5 Medical History

Medical history will be listed for the safety population.

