5.4 Adverse Events of Special Interest (AESI)

Analyses of AESI will include aspiration, aspiration pneumonia, choking, and dysphagia. Incidences of subjects reporting AESI will be reported for each treatment session. Details of AESIs will be listed for individual subjects will be listed.

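### The planned AESI summaries do not use the screening evaluation of the same four conditions, so they mix new onset with worsening of pre-existing dysphagia or choking

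*Protocol*

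**What the plan says.** - **Endpoint.** Protocol 9.1: "Occurrence of adverse events of special interest (i.e., aspiration, aspiration pneumonia, choking, dysphagia) at each study visit as assessed by the Investigator".
- **Baseline evaluation.** Protocol 16.2.4 states that presence or "prior history of aspiration, aspiration pneumonia, choking, and dysphagia must be taken at screening and captured in the" source documents and eCRF. It adds that "the definitions for diagnosis and intensity identified below should be used for baseline evaluations". Protocol 16.1 says that "the definitions for the diagnosis and intensity provided in Section 16.2.4 should be used for" the baseline evaluation and every later one.
- **Stated use of the baseline.** Protocol 16.2.4: "This thorough baseline evaluation will assist the Investigator in determining, based on a clinical evaluation, whether or not occurrences of aspiration" and the other three conditions qualify as adverse events.
- **Eligibility.** The amendment summary (Protocol 1) records that "Specific criteria excluding subjects with moderate to severe dysphagia or choking within the last 6 months prior to screening have been removed". Exclusion criterion 1 in Protocol 11.1.2 now turns on aspiration risk, with an allowance where a PEG or G-tube is judged to control it.
- **Analysis.** SAP 5.4: "Incidences of subjects reporting AESI will be reported for each treatment session", plus a listing by subject. SAP 2.9.2 adds frequencies by body system and preferred term, and summaries of adverse event severity and relationship. SAP 3.5: "Medical history will be listed for the safety population".

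**The concern.** The study has one arm, so each subject's own state at entry is the only internal reference for events that the underlying diseases also cause. Protocol 1 itself calls dysphagia common in neurological disorders and especially frequent in ALS, so affected subjects are to be expected. A proportion with dysphagia in a session can then contain two kinds of subject: one who swallowed normally at entry and one who was already impaired and got worse. These answer different safety questions. The second question matters more since the amendment dropped the specific dysphagia and choking exclusions. The data needed to tell them apart are collected, but no summary in the SAP text uses them.

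**Working it through.** The documents give no AESI rate and no sample size calculation (SAP 2.5), so there is no figure to reproduce. The check is a comparison of sections, followed by an illustration.

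**Comparison of sections**

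1. *Same definitions before and after.* Protocol 16.1 and 16.2.4 apply one set of diagnosis and intensity definitions at screening and afterwards. Baseline and on-study grades are meant to be comparable.
2. *Affected subjects can enter.* Criterion 1 in Protocol 11.1.2 does not exclude dysphagia or choking as such. It excludes moderate to high aspiration risk on any of four grounds, unless a PEG or G-tube is judged to control that risk.
3. *Both kinds of event share one numerator.* Protocol 16.2.1 counts exacerbation of an existing condition as an adverse event. SAP 2.9.2 defines treatment emergence by date relative to the first injection, with no reference to baseline state.
4. *The summaries stop at frequency.* SAP 2.9.2 and 5.4 and Protocol 17.7 give AESI frequencies by session and preferred term. SAP 2.6.3 mentions the baseline history only as something recorded. The baseline summaries in SAP 3.4 cover diagnosis, prior therapy and the sialorrhea scales.
5. *Other safety measures do use a baseline.* SAP 2.9.2 gives laboratory tests shift tables, and gives vital signs, weight and C-SSRS a change from pre-injection.

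**Illustration (assumed counts)**

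Take N = 187 (SAP 2.5) and assume x = 19 subjects report an AESI: 19/187 = 10.2% (Clopper-Pearson 95% CI 6.2 to 15.4). Let n_u and n_a be the numbers unaffected and affected at baseline, and k_u + k_a = x. The pooled table fixes only x. The new-onset rate k_u/n_u can therefore lie anywhere from 0 to x/n_u, and the worsening rate k_a/n_a anywhere from 0 to x/n_a.

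| Assumed affected at baseline | n_a | n_u | New onset possible | Worsening possible |
|---|---|---|---|---|
| 20% | 37 | 150 | 0 to 19/150 = 12.7% | 0 to 19/37 = 51.4% |
| 40% | 75 | 112 | 0 to 19/112 = 17.0% | 0 to 19/75 = 25.3% |
| 60% | 112 | 75 | 0 to 19/75 = 25.3% | 0 to 19/112 = 17.0% |

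At 40% affected, the new-onset range is 0 to 8.0% if x = 9 and 0 to 25.0% if x = 28. A split table would replace the range with estimates. For example, with k_u = 9 and k_a = 10, new onset is 9/112 = 8.0% (95% CI 3.7 to 14.7) and worsening is 10/75 = 13.3% (6.6 to 23.2).

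**Direction**

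The pooled risk is π·r_a + (1 − π)·r_u, where π is the affected share and r_a and r_u are the risks in affected and unaffected subjects. Take π = 30%:

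- r_a = 15%, r_u = 3%: 0.30 × 0.15 + 0.70 × 0.03 = 6.6%, above the risk in unaffected subjects.
- r_a = 2%, r_u = 3%: 0.30 × 0.02 + 0.70 × 0.03 = 2.7%, below it.
- r_a = r_u: no distortion.

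The documents do not say which case applies.

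**The case against.** The case for leaving the plan alone has real force.

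- **The listings allow the split.** AESIs and medical history are both listed by subject, and the baseline is in the eCRF. This stands: no data are missing, only a summary. A reader might infer that new onset and worsening cannot be told apart in this study. That is true only of the planned summaries.
- **The baseline is already used.** The Investigator uses it to decide whether an occurrence is an adverse event, and Protocol 16.2.1 lets anticipated fluctuations go unreported. This also stands, so it would be wrong to call the baseline unused. But that decision does not label a counted event as new or worsened. In addition, Protocol 16.2.4.3 words the dysphagia diagnosis in terms of new onset while 16.2.1 counts exacerbations, so sites may differ on what they report.
- **The tables go beyond one pooled figure.** Preferred term and severity are tabulated. On-study severity alone, however, does not show change from entry.
- **Other planned outputs might cover it.** SAP 3.4 implies that medical history is summarised, whereas 3.5 only lists it; neither would link baseline to AESIs. The Protocol 17.7 summary without disease-related events filters on causality, not on baseline. The SAP's table shells (its Section 7) were not in the text available to me, so the statement covers the SAP and protocol text only.
- **A graded shift does not suit every term.** This stands for aspiration pneumonia, which is episodic and is exclusionary if it occurred within 6 months before screening. PEG or G-tube status at entry is also not a named data item in Protocol 16.1 or 16.2.4.

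**Conclusion.** The point holds as a gap in the planned summaries. The conditions are evaluated at screening with the AESI definitions, affected subjects can enter under the aspiration-risk conditions, and both new events and exacerbations count. No summary described in the SAP text separates them.

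The size and direction of the mixing are unknown. The ranges in the working rest on assumed counts and prevalences, and show only how little a pooled figure pins down.

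Two stronger readings are not supported:

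- A reader might infer that pooling overstates risk in unaffected subjects and understates it in affected ones. That requires a higher recorded risk in affected subjects. The documents give no such figure, and the new-onset wording for dysphagia could push the other way.
- A reader might take the amendment to admit anyone with moderate to severe dysphagia. Criterion 1 still excludes moderate to high aspiration risk unless it is judged controlled by a PEG or G-tube.

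This is a cheap improvement to the analysis. It is not a flaw that undermines the safety conclusions.

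**What to change.** In SAP 5.4:

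1. For each AESI term, report incidence by session and over the whole study, separately for subjects with and without that condition at screening. Show the stratum denominators.
2. For dysphagia and choking, cross-tabulate baseline intensity (none, mild, moderate, severe) against worst on-study intensity.
3. For aspiration and aspiration pneumonia, split by prior history yes or no only.
4. Add a split by PEG or G-tube at entry only if that status is recorded.

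In SAP 3.4 or 3.5, summarise baseline status for the four conditions as well as listing it, and reconcile the two sections on whether medical history is summarised or listed.

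The cost is a few descriptive tables. Apart from the PEG or G-tube split, they use data that the protocol already requires. Some cells will be small, so show counts with denominators and do no testing.

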9.2 Effectiveness Endpoints

- Unstimulated salivary flow rate (USFR) (Assessor) at each study visit;
- Clinical Global Impression of Severity (CGI-S) and Change (CGI-C) (Assessor) at each study visit;
- DFSS-I (Assessor) at each study visit;
- DFSS as assessed via subject's diary at each assessment time point;
- Patient Global Impression of Severity (PGI-S) and Change (PGI-C) at each study visit; and
- Drooling Impact Score (DIS) (Subject) at each study visit.

10 STUDY DESIGN

This is a Phase 3, multicenter, open-label, outpatient study of safety/tolerability and effectiveness of repeated doses (3,500 Units) of MYOBLOC in adult subjects with troublesome sialorrhea over a maximum 1-year duration. The study population will be comprised of a mixture of patient populations including, but not limited to, subjects with PD-related sialorrhea, subjects with sialorrhea secondary to other non-PD conditions (e.g., cerebral palsy, ALS, stroke, traumatic brain injury), or sialorrhea secondary to oral cancer or medications (e.g., neuroleptics). The study is planned to be conducted at 20 or

more study sites and include approximately 120 to 200 male and female subjects (or until enough subjects have completed to meet FDA safety database requirements; see further details in Section 11.1). A diagnosis of PD fulfills the UK Parkinson's Disease Society Brain Bank diagnostic criteria, and a diagnosis of ALS fulfills the El Escorial World Federation of Neurology criteria.

The planned duration of participation for each subject is a minimum of 26 weeks and a maximum of 52 weeks, excluding the screening period, which can last up to 21 days, with study drug injected at approximately 13-week (± 2 weeks) intervals for a maximum of 4 treatments over this 1-year period.

During the screening period, the following will be assessed to evaluate the subject's eligibility to participate in the study: inclusion and exclusion criteria; medical, surgical, and medication history; presence or prior history of aspiration, aspiration pneumonia, choking, and/or dysphagia; complete physical exam (including vital signs, height, and weight); neurologic exam; dental exam; clinical laboratory testing; urine pregnancy testing (females of childbearing potential only); and forced vital capacity (FVC) (if warranted, such as in ALS patients). All subjects successfully completing screening will have the following procedures/assessments conducted at baseline (Day 1) before the first injection of MYOBLOC: brief physical exam (including vital signs); FVC (if warranted); neurologic exam; Columbia Suicide Severity Rate Scale (C-SSRS); oral exam; saliva production quantitatively determined via USFR; qualitative assessments by the Investigator including CGI-S and DFSS-I; subject assessments including PGI-S, DFSS, DIS; and urine pregnancy test (result must be negative to proceed with the injection). Those subjects who satisfy all eligibility criteria may receive a dose of MYOBLOC (3,500 Units) via injections into the submandibular and parotid glands on Day 1. Subjects will be contacted by telephone 24 hours post-injection to inquire about their health status.

Subsequent study visits will occur at Weeks 4 (± 3 days), 8 (± 3 days), 13 (± 2 weeks), 17 (± 5 days), 26 (± 2 weeks), 30 (± 5 days), 39 (± 2 weeks), 43 (± 5 days), and 52 (± 2 weeks), with safety and effectiveness assessments made as detailed in the Schedule of Assessments in Table 2 in Section 14.1; telephone follow up will be done at Weeks 14 (± 1 day), 21 (± 5 days), 27 (± 1 day), 34 (± 5 days), 40 (± 1 day), and 47 (± 5 days)

Injections at each treatment session will be done when the subject returns to baseline status as determined by the Principal Investigator, with a minimum interval of 11 weeks from the prior injection but no later than 15 weeks from the prior injection. If after the first treatment of 3,500 Units the subject develops intolerable side effects, but still wishes to remain in the

study, the Investigator has the discretion to decrease subsequent doses, but to no less than a total dose of 2,500 Units.

11 SELECTION OF SUBJECTS

11.1 Population Base

Adult subjects with troublesome sialorrhea and a minimum USFR (as defined in Section 11.1.1) are eligible for the study. Enrollment will continue until a minimum total of 300 subjects (across this protocol and the prior MYOBLOC clinical trial in sialorrhea expected to meet FDA safety database requirements) have been treated with clinically relevant doses ($\geq 2,500$ Units) of MYOBLOC for a minimum of 6 months and 100 subjects treated with MYOBLOC at clinically relevant doses for a minimum of 1 year. Sixty of the 100 subjects must be treated with 3,500 Units for the minimum period of 6 months. It is estimated that approximately 120 to 200 subjects will be enrolled in this open-label study in order to accrue a sufficiently large safety database for evaluation. The study population should be comprised of a mixture of patient populations including, but not limited to, subjects with PD-related sialorrhea, subjects with sialorrhea secondary to other non-PD conditions (e.g., cerebral palsy, ALS, stroke, traumatic brain injury), or sialorrhea secondary to oral cancer or medications (e.g., neuroleptics). Entry into the study is open to both men and women and to all racial and ethnic subgroups.

11.1.1 Inclusion Criteria

To be eligible for participation, subjects with troublesome sialorrhea must meet all of the following criteria:

1. Able to read and provide written informed consent before enrollment into the study, or the subject's caregiver (Legally Authorized Representative) can provide written informed consent.
2. Male or female, 18 to 85 years of age (inclusive).
3. Seeking treatment for troublesome sialorrhea for at least 3 months that is occurring secondary to any disorder or related to any cause, including, but not limited to, PD, adult cerebral palsy, ALS, stroke, traumatic brain injury, oral cancer, and side effects of other medications. Note: A diagnosis of PD fulfills the UK Parkinson's Disease Society Brain Bank diagnostic criteria. A diagnosis of ALS fulfills the El Escorial World Federation of Neurology criteria.
4. Minimum USFR of 0.2 g/min at screening (unstimulated normal rate is 0.3 g/min) [Wang 1998].
5. Minimum Investigator's DFSS score of 4 (range 2-9, a score of 2 = "never drools") at screening.

6. Ability and availability to participate in the study for up to 1 year (ALS subjects: ability and availability to participate in the study for at least 6 months), based on overall health of the subject and disease prognosis, as applicable, in the opinion of the Investigator, and able to comply with all requirements of the protocol, including completion of study questionnaires. A caregiver may be designated to assist with assessments.

11.1.2 Exclusion Criteria

Subjects who meet any of the following criteria will not be allowed to participate:

1. A moderate to high risk of aspiration will exclude participation in this study. Moderate to high risk of aspiration is defined by any one of the following:
 - History of aspiration pneumonia in the last 6 months before screening
 - Speech pathologist and/or formal swallowing test (e.g., with barium, endoscopy, dynamic swallowing study, imaging study, fiber-optic endoscopic swallowing evaluation or other imaging scan) that concludes that a moderate to severe risk of aspiration exists
 - Due to perceived risk of aspiration, a health care professional has recommended PEG or G-tube but subject declined
 - In the Investigator's clinical judgment, the subject is at moderate to high risk of aspiration.Subjects whose risk of aspiration are judged by the Investigator to be satisfactorily controlled by placement of PEG tube or G-tube for nutritional support are eligible to participate.
2. Respiratory FVC of <20% of predicted. FVC will be tested in all ALS subjects, and also in other subjects at Investigator discretion if warranted.
3. Prior botulinum toxin type A or B treatment in the salivary gland(s) identified for treatment in this study within 24 weeks before screening. Prior botulinum toxin type A or B treatment into other anatomical regions not selected for treatment in this study is not exclusionary, but must have occurred at least 12 weeks before screening.
 - In the Investigator's assessment, prior toxin exposure must have been well tolerated and without any significant long-term side effects in the case of repeated prior exposure. Subjects should be excluded if, in the Investigator's opinion, the subject failed to respond to previous treatment with botulinum toxin. Subjects should not receive nor have any plans for receiving any botulinum toxin treatment, other than the study drug (MYOBLOC), during the entire course of the study (from the point the informed consent is signed until subject's participation is complete).
4. Prior salivary gland surgery.
5. Concomitant use, or exposure within 5 half lives of screening, of aminoglycoside antibiotics, curare-like agents, or other agents that interfere with neuromuscular function.

6. Current treatment or treatment at any time during the study with Coumadin[®] (warfarin) or similar anti-coagulant medications. Anti-platelet medications are not specifically exclusionary.
7. Anticipated or scheduled surgery during the study period. A PEG tube/G tube may be placed for nutritional support at any time during the study and will not exclude the subject from continued study participation.
8. Major surgery (requiring general anesthesia, except PEG tube/G-tube placement) within the previous 6 months before screening. If surgery occurred more recently than 6 months before screening, Investigator must have sufficient documentation to demonstrate the subject has fully recovered and stabilized. Prior movement disorder-related surgery (e.g., pallidotomy, thalamic/subthalamic/pallidal deep brain stimulation) will not exclude the subject, provided the surgery was performed at least 6 months before screening.
9. Anticholinergic and antihistamine medication eligibility restrictions (see also Section 16.10):
 - Oral/transdermal pharmacologic treatment (specifically antihistamines and those medications with anticholinergic properties) **for troublesome sialorrhea** must be discontinued during the 30-day period before screening and are not allowed in the entire duration of the study, except ALS subjects as allowed herein. For ALS subjects only: such medications for the treatment of sialorrhea are allowed; however, conversion to, or continuation of, a short-acting medication (duration of action of approximately 8 hours or less) is required at a stable dose/regimen at least 2 weeks before the first injection of study drug (i.e., Day 1 of Treatment Session 1). The short-acting anti-cholinergic medication for the treatment of sialorrhea may be continued throughout screening and study participation provided that the ALS subject agrees to hold the medication for at least 8 hours before the screening, baseline, and all subsequent study visits, so that the effectiveness and safety of the study drug can be properly evaluated.
 - Antihistamines and anticholinergic medications taken **for a non-sialorrhea condition** should be avoided as much as possible, but are not exclusionary.
10. Evidence of any clinically significant neurologic disease (e.g., myasthenia gravis, Lambert-Eaton syndrome), cardiovascular, hematologic (including bleeding diathesis), hepatic, renal, gastrointestinal, endocrine, pulmonary, musculoskeletal, psychiatric disease or condition, or dental condition, which in the judgment of the Investigator or screening dentist would put the subject at risk while in the study, could influence the results of the study, or negatively impact the subject's ability to participate in the study
11. Pregnancy or lactation
 - As assessed by the Investigator, females of childbearing potential must agree to practice a medically acceptable method of contraception (e.g., intrauterine device, hormonal contraception started at least one full cycle before study enrollment or

- barrier method in conjunction with spermicide) for the duration of the study (including 2 months after study completion). For the purposes of this study, all females are considered to be of childbearing potential unless they are confirmed by the Investigator to be post-menopausal (at least 1 year since last menses), biologically sterile, or surgically sterile (e.g., s/p hysterectomy, bilateral oophorectomy, tubal ligation).
12. History of drug or alcohol abuse currently or within the previous 6 months, as determined by the Investigator.
 13. Current infection at the sialorrhea treatment injection site(s).
 14. Participation in another clinical drug, device, or biological agent study within 30 days of screening or while participating in this study.
 15. Any other condition or clinical finding that, in the opinion of the Investigator and/or the Sponsor, is determined to be unsuitable for enrollment into this study.

